Methadone in Pediatric Anesthesia II

PI: [name] MD, MBA
Associate Professor,
Director of Quality Improvement,
Department of Anesthesiology, BO 8054
[contact]
[contact]

Co-PI: [name] PhD
Russell D. and Mary B. Shelden Professor of Anesthesiology
Director, Division of Clinical and Translational Research
Department of Anesthesiology, Box 8054
T [contact]
F [contact]
[contact]

Co-Investigators: [name] MD
Associate Professor of Anesthesiology
Box 8054,
[contact]

Original: 02/02/2013
Amendment 1: 12/5/13
Amendment 2: 4/16/14
Amendment 3: 09/10/2014

Amendment 1, 12/5/2013: Administration of PROMIS questionnaire to be administered by the research team to the patient on a tablet device.

Rationale: To help determine patient's preoperative expectations and functional status as impacted by their medical condition requiring this surgical procedure.

CONFIDENTIAL

Amendment 2, 4/16/2014: Administration of a questionnaire to the participant's parent or legal guardian

Rationale: To help determine from the primary caregiver the influence of the environment, social and psychological, on post-operative pain.

CONFIDENTIAL

Amendment 3, 09/10/2014: Change in dosage range for intraoperative administration of methadone from 0.4-0.5mg/kg Ideal Body Weight to 0.3 – 0.5mg/kg Ideal Body Weight (IBW)

Rationale: Postoperative management of pain for the pediatric spinal surgery population has changed over the course of time since the completion of our last research project (HRPO# 201107357). The previous study had demonstrated that 0.3mg/kg methadone was not effective in reducing postoperative opioid consumption. Currently, patients are prescribed additional drugs such as gabapentin and methocarbamol, with potential for interaction with all opioids. Based on our observations with this current protocol to date, we anticipate that escalation of methadone dosages beyond 0.4mg/kg (ideal body weight) may not be required. We feel that routine postoperative use of gabapentin and methocarbamol require re-evaluation of intraoperative methadone dosing at 0.3mg/kg (IBW) for this population under current standard of care pain management.

CONFIDENTIAL

Abstract

The μ -opioid receptor agonist methadone is frequently used in adult anesthesia and adult pain therapy. Methadone has an extremely long half-life, which confers therapeutic advantage by providing more stable plasma concentrations and long-lasting pain relief. Methadone perioperative pharmacokinetics in adults is well characterized. Methadone is also frequently used in children. Previous work by our group demonstrated that pharmacokinetics of methadone in adolescents are very similar to that in adults, but that doses used for major spinal surgery (0.1-0.3 mg/kg) were insufficient to have a significant opioid-sparing effect. This current investigation aims to study opioid sparing effects of higher doses of methadone (0.3 - 0.5 mg/kg) in adolescents undergoing posterior spinal fusion. Additionally, we will determine the pharmacokinetics of the higher doses of IV methadone administered intra-operatively.

CONFIDENTIAL

SYNOPSIS

Study Title	Methadone in Pediatric Anesthesia II
Objective	Multiple arm, randomized controlled trial to evaluate the efficacy of a single dose of intraoperative methadone in reducing post-operative pain and opioid consumption in adolescents undergoing posterior spinal fusion. Our secondary goal is to determine the pharmacokinetics of IV methadone in children (0.3 - 0.5 mg/kg).
Study Period	Planned enrollment duration: Approximately 2 years. Planned study duration: Approximately 6 days per subject
Number of Patients	60 evaluable subjects
Study Medication Administration	60 evaluable patients will be randomized 2:1 to receive intraoperative IV methadone HCL, 0.3 – 0.5mg/kg, or serve as controls and will not receive any methadone. Control subjects will receive standard of care treatment per the attending anesthesiologist.
Study Design	Randomized, controlled, modified, Dixon up and down dose-finding design (1). Patients receive standard monitoring for anesthesia and postoperative care. Surgical and anesthesia (except for opioid use) care are not altered for study purposes. All patients are induced by propofol and muscle relaxants. In the first cohort, subjects are randomized 1:2 to either control (standard intraop opioid at anesthesiologists' discretion) or methadone HCl (0.4 mg/kg ideal body weight, IBW). Based on an interim analysis for the initial treatment dose (0.4mg/kg), the second cohort will be randomized 1:2 to either control (standard intraop opioid) or methadone HCl (0.3 mg/kg ideal body weight, IBW). Subjects in the study groups will receive methadone (IV bolus, after induction of anesthesia) as their primary intraoperative opioid, rather than leaving the choice of intraoperative opioid to the anesthesiologist. Intraoperative breakthrough pain will be treated at the discretion of the anesthesiologist with fentanyl. In the control groups, intraoperative opioid administration will be left at the discretion of the anesthesia providers. Patient controlled analgesia as prescribed by the clinical team, using hydromorphone or morphine, will be used to treat postoperative pain relief.
Inclusion and Exclusion Criteria	Inclusion Criteria 1. Age 11-18 years 2. Undergoing general anesthesia and idiopathic posterior spinal fusion surgery with anticipated postop inpatient stay of > 3 days 3. Signed, written, informed consent from legal guardians and assent from patient Exclusion Criteria 1. History of liver or kidney disease. 2. Females who are pregnant or nursing. 3. Developmental delay and/or neuromuscular scoliosis
Measurements	Total intraoperative and postoperative care unit (PACU) opioid administration will be recorded from the patient's medical record. Daily opioid consumption will be calculated from the PCA utilization and electronic medical records (EMRs) for up to 6 postoperative days. Pain intensity will be assessed using the Wong-Baker FACES scale. Pain relief is also assessed using a Colored-Visual Analog Scale. Blood and urine samples will be collected for 96 hrs after methadone dosing for determination of methadone and metabolite concentrations by HPLC-mass spectrometry. Subjects will be genotyped for major polymorphisms of the methadone metabolizing enzyme CYP2B6.
Statistical Methodology	Demographics data including race, sex, and age will be analyzed. Baseline characteristics of the cohort will be described. Results will be expressed as the mean and standard deviation.
Outcomes	Primary: Intraoperative, postoperative and daily cumulative opioid utilization Secondary: Methadone and metabolite enantiomers plasma AUC, maximum concentration, metabolite /methadone AUC ratios, metabolite formation clearance correlation of methadone enantiomer clearances and metabolite formation clearances, influence of CYP2B6*6 hetero or homozygote genotype

on above primary and secondary outcomes

1. Specific Aims.

- 1.1. To study the effects of a single dose of methadone on postoperative pain and opioid consumption in pediatric surgical patients.
- 1.2. Determine the pharmacokinetics of IV methadone (0.3-0.5 mg/kg) in children
- 1.3. Determine cytochrome P4502B6 (CYP2B6) genotype in patients receiving methadone, and any relationship to methadone clearance.
- 1.4. Determine from the primary caregiver the influence of the environment, social and psychological, on post-operative pain.

2. Background

Inadequate pain relief has a significant psychological impact upon children, including alterations in their perceptions of future painful experiences and medical procedures (1). The psychological ramifications of pediatric pain include posttraumatic stress disorder, lack of adherence to treatment, poor coping skills, changes in accuracy in the self-report of pain, and lack of trust in health-care providers (2). The degree to which this pain is controlled impacts the ability of patients to cope with the next pain episode. Patients undergoing major spine surgery experience severe pain in the postoperative period, which may increase morbidity and the incidence of complications, as well as prolong postoperative rehabilitation. Postoperative pain itself is a risk factor for development of chronic pain syndromes(3,4).

Methadone is a μ opioid agonist which is highly efficacious in the treatment of acute, chronic, neuropathic, and cancer pain(5). In adults it is increasingly being used as a first-line analgesic. Methadone is highly efficacious in adult anesthesia and postoperative pain(6,7). The typical dose for adult anesthesia is 20 mg (nominally 0.3 mg/kg) at the beginning of anesthesia. Methadone is advantageous because it has slow elimination, resulting in prolonged effect and significantly diminished need for postoperative analgesics. Reducing postop opioid analgesic use also decreases the potential for opioid-related side effects. Methadone has a long half-life, averaging 24-36 hours in healthy adults and adolescent patients (12). It has no active metabolites or pro-drug forms. Methadone is metabolized in the liver by cytochrome P450 CYP2B6 (8-10). Methadone is also widely used in children, particularly in pain treatment(11). In infants and children younger than 10 yrs (mean age 4 yrs), the initial daily dose of methadone did not exceed 0.2–0.4 mg/kg/day, and daily methadone doses rarely exceeded 0.6 mg/kg.

Perioperative analgesia remains a major challenge for physicians who care for patients undergoing complex spine surgery. Many patients are controlled by opioid analgesic that can result in postoperative adverse events. We propose to compare the two different doses of methadone in reducing

the postoperative opioid consumption and reduction in pain scores.

A recent study by our group demonstrated that the pharmacokinetics of methadone enantiomer disposition in adolescents were similar to that of healthy adults (12). Another study by Stemland et al used a three compartmental model to analyze time-concentrations profile of single dose of 0.25mg/kg of methadone. They concluded that the pharmacokinetic profile in adolescents was similar to that of adults. They also observed a rapid redistribution after single bolus of methadone, hence producing inadequate plasma concentrations of the drug for postoperative analgesia. This suggests that in order to improve efficacy of methadone, higher dose than 0.3 mg/kg of methadone or continuous infusion of methadone may be needed (13).

Evaluating the role of methadone in pediatric spinal surgery patients is advantageous because 1) high dose of opioids are routinely used during and after the surgery, 2) methadone is one of the commonly used opioids for this surgery, 3) an arterial catheter or a second IV catheter is needed for the surgery and can be used to draw blood samples, 4) prolonged analgesia from methadone is expected to decrease the need for additional opioids.

Assessment of pain has become standard practice in the treatment of pediatric patients. Several pain scales including the Wong-Baker FACES scale, the Oucher Scale and the Visual Analog Scale (VAS) have been USED in children who were experiencing pain (14,15).

In this study, we propose to evaluate postoperative opioid consumption, pain intensity and pain relief in pediatric patients undergoing posterior spinal fusion who will receive a single dose of methadone during surgery. In addition, we will study dose effect of ing various doses of methadone, between 0.3 – 0.5mg/kg IBW. Secondarily, we will determine the pharmacokinetics of higher doses of IV methadone in children who are undergoing anesthesia and surgery. Lastly, we will determine the role of CYP2B6 genotype on methadone pharmacokinetics.

3. Drug Information

Methadone hydrochloride is a synthetic μ -agonist with multiple actions qualitatively similar to those of morphine. Onset of effect is about 2-10 min for parenteral dosing. Methadone is primarily metabolized by N-demethylation to an inactive metabolite, 2-ethylidene-1,5-dimethyl-3,3-diphenylpyrrolidene (EDDP). In vitro, cytochrome P450 enzymes, primarily CYP3A4 and CYP2B6 are responsible for conversion of methadone to EDDP and other inactive metabolites. In vivo, CYP2B6 is a major determinant of metabolism to inactive metabolites which are excreted mainly in the urine. The terminal half-life ($T_{1/2}$) in healthy children averages 24-36 hrs. Like adults, in teenage children, most common side effect of methadone, like other opioids, is sedation, nausea and vomiting. Respiratory depression is the chief hazard associated with methadone, like all opioids. QT prolongation and serious arrhythmia have been observed during treatment with methadone and have been associated with doses

>200 mg/day(16).

4. Eligibility

4.1. Inclusion Criteria.

- 4.1.1. Age 11-18 years
- 4.1.2. Undergoing general anesthesia and idiopathic posterior spinal surgery with anticipated postop inpatient stay of > 3 days
- 4.1.3. Signed, written, informed consent from legal guardians and assent from patient

4.2. Exclusion Criteria.

- 4.2.1. History of or known liver or kidney disease.
- 4.2.2. Females who are pregnant or nursing.
- 4.2.3. Children with developmental delay
- 4.2.4. Children undergoing surgery for neuromuscular scoliosis

5. Enrollment

- 5.1. Subjects and parents/guardians will be approached prior to surgery. Patients will be consented for participation and enrolled in the study by study personnel.

6. Methods

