6.1. Preoperative and Intraoperative Period

Parents and patients will be asked to complete a questionnaire prior to the child's surgery. This will take approximately 5 minutes. Participants can choose to complete the survey and not participate in the randomized part of the study. The questionnaire is to determine if factors such as anxiety and social economic attributes interact with each other prior to surgery. If only participating in the questionnaire information regarding demographic data, pain scores and pain treatment will be collected from the patients' medical record.

Patients will receive standard physiologic monitoring for anesthesia and postoperative care. Using a modified Dixon up and down dose finding method, subjects in the first cohort are randomized 1:2 to receive either control (standard intraop opioid) or methadone HCl (0.4 mg/kg ideal body weight, IBW). In the second cohort, subjects are randomized 1:2 to receive either control (standard intraop opioid) or methadone HCl (0.3 mg/kg ideal body weight, IBW).

Anesthesia and surgical care will not be altered for the purposes of this investigation, except that subjects in groups I and II, will receive methadone as their intraoperative opioid, rather than leaving the choice of intraoperative opioid to the anesthesiologist (patients typically may get methadone or any other opioid). The control group patients will receive intraoperative analgesia with opioids other than methadone left at the discretion of their anesthesiologist. Additional

randomized cohorts may be included to study IV methadone HCl doses within the range of 0.3 – 0.5mg/kg IBW, based on interim study findings and analysis.

6.2. *Administration of Study Medication.*

Methadone is administered as an IV bolus after induction of anesthesia and after an arterial line is placed. Methadone hydrochloride is available commercially as a solution for injection of 10 mg/ml. Based on our experience, we believe that additional postoperative opioids will still be needed, but that increasing methadone doses will result in lessened postoperative opioid use.

6.3. *Assessments.*

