9.1. Primary Assessment

9.1.1. Overall morphine (equivalents) consumption for each patient during hospitalization

9.1.2. Absolute pain scores and pain relief scores

9.2. Secondary Assessments

9.2.1. Methadone clearance

9.2.2. Maximum plasma methadone concentration

9.2.3. Area under the curve (AUC) of plasma EDDP vs time

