9.2.4. Maximum plasma EDDP concentration

9.2.5. AUC (plasma EDDP)/AUC (plasma methadone)

9.2.6. Cmax (plasma EDDP)/Cmax (plasma methadone)

9.2.7. Urine concentration of methadone and EDDP

9.2.8. Side effects of opioids

9.3. Analysis.

9.3.1. Sample Size- we decided to use our pilot study data which looked into the pharmacokinetics of methadone in pediatric surgical patients attending St. Louis Children Hospital. This is actually the pooling place for the present study and therefore the information provided is a "true" sample of the data to be collected. The pilot study revealed that patients undergoing spinal fusion surgery used an average of 274 mg of morphine equivalents within 72 hours post-surgery with a standard deviation of 82 mg. Based on this information and assuming a 2-sided test of two independent sample means with α 0.05, we were able to estimate that the proposed study will have at least 80% power to detect 30% decrease in the total postoperative consumption of morphine or morphine equivalents among the patients assigned to the two treatment groups combined when compared to the control group

patients. Specifically, with a total sample of approx. 60 patients assigned equally across study groups (1:2 randomization), we will have adequate statistical power to detect a clinically meaningful reduction of opioid use in patients receiving a single dose of methadone before incision.

To study the effect size between two groups, power calculations were made with alternative mean differences in morphine consumption over 72 hours post-surgery with assumed variation range and a 2-sided test with $\alpha = 0.05$. Based on our conservative assumptions, we found that, with a sample as small as 20 in each group, we will have 80% power to detect a minimum difference between 10 and 20 mg of morphine use, depending on the observed variability between the two groups.

9.3.2. Statistical Analysis- Baseline characteristics of the cohort will be described. Demographics data including race, sex, and age at study entry will be analyzed using chi-square and t- test appropriate. Total daily opioid consumption and pain scores using both Wong-Baker FACES and colored visual analogue scale, will be compared between the groups. Outcome measures will be expressed by the mean and standard deviation. Group outcomes will be compared across the two or three groups, using t-test and/or analysis of variance, ANOVA and MANCOVA to account for potential cofounders.

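### The plan is labelled a modified Dixon up-and-down dose-finding design, but it has no response that moves the dose, no step criterion and no target-dose estimator, so it cannot yield an ED50 or an effective dose

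*Combined protocol and SAP*

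**What the plan says.** **Label.** The Synopsis (Study Design) gives "Randomized, controlled, modified, Dixon up and down dose-finding design (1", where the closing figure is a citation. Section 6.1 repeats it: "Using a modified Dixon up and down dose finding method, subjects in the first cohort are randomized 1:2".

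**How the dose changes.** The first cohort compares control with 0.4 mg/kg. For the next, the Synopsis says "Based on an interim analysis for the initial treatment dose (0.4mg/kg), the second cohort will be randomized 1:2" to control or 0.3 mg/kg. Section 6.1 gives the same two cohorts without mentioning a condition, then adds that further "randomized cohorts may be included to study IV methadone HCl doses within the range of 0.3 – 0.5mg/kg IBW, based on interim study findings".

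**Outcomes.** The primary assessments are "Overall morphine (equivalents) consumption for each patient during hospitalization" (9.1.1) and "Absolute pain scores and pain relief scores" (9.1.2).

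**Analysis.** Section 9.3.2 says "Outcome measures will be expressed by the mean and standard deviation" and "Group outcomes will be compared across the two or three groups, using t-test and/or analysis of variance, ANOVA and MANCOVA". Section 9.3.1 bases the sample size on both methadone groups pooled against control.

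**The concern.** An up-and-down design sets the next dose from an observed response under a fixed rule, and estimates a target dose from the resulting sequence. If the rule and the estimator are missing, the name describes a property that the trial does not have.

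What is at stake is the interpretation of the dose results. A report that keeps the label could be read as having identified a sufficient dose for adolescents, when the plan supports only comparisons of group means at the doses given. Those doses are also studied one after another, so a plain contrast between them carries any change in care over time.

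**Working it through.** **1. Parts of an up-and-down design, set against the plan**

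- *Response that drives dosing.* Outcomes are recorded for each patient, but as opioid totals and scale scores. No threshold makes a patient or a cohort a success or a failure.
- *Step criterion.* An interim analysis is mentioned, without timing, content or decision criterion, and the dose that follows it is already named. Further cohorts have no stated trigger, step size, cohort size or stopping point.
- *Estimator.* Section 9.3.2 lists the t-test, ANOVA and MANCOVA. Dose enters a model only in 9.3.3, for pharmacokinetic linearity.
- *Method by reference.* The citation attached to the label is reference 1, a paper on relieving pain and anxiety in paediatric emergency care. It does not stand in for a description of the design.

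**2. The plan's own power figure**

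Inputs from 9.3.1: mean 274 mg and SD 82 mg over 72 hours, a 30% reduction, two-sided α 0.05, about 60 patients at 1:2 (20 control, 40 methadone).

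- Difference: 0.30 × 274 = 82.2 mg.
- Standard error: 82 × √(1/20 + 1/40) = 22.46 mg, and 82.2 / 22.46 = 3.66.
- Power: Φ(3.66 − 1.96) = 95.5% by the normal approximation, 94.9% by the noncentral t.

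The stated figure of at least 80% is correct for pooled methadone against control. It says nothing about choosing between doses.

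**3. One dose against the other**

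Assumption: the 40 methadone patients split evenly, 20 per dose.

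- Detectable difference at 80% power: (1.960 + 0.842) × 82 × √(2/20) = 72.6 mg by the normal approximation, 74.5 mg by the noncentral t.
- 74.5 / 274 = 27%, nearly the whole reduction that the trial is powered to find against control.
- Power for assumed between-dose differences of 10%, 15% and 20% of 274 mg (27.4, 41.1 and 54.8 mg): 18%, 34% and 54%.

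Section 9.3.1 also claims 80% power for 10 to 20 mg with 20 per group. That would need an SD of about 11 to 22 mg. At 82 mg the power is 7% and 12%, so that statement cannot support the dose comparison.

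**4. Each dose against its own controls**

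Assumption: 60 patients split evenly over two cohorts, 10 control and 20 methadone in each.

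- Standard error: 82 × √(1/10 + 1/20) = 31.8 mg. The 95% CI half-width is 2.048 × 31.8 ≈ 65 mg (28 degrees of freedom).
- Power for 82.2 mg: 70%, ranging from 53% at 7 v 13 to 87% at 15 v 30.

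Comparing the doses through these within-cohort differences removes the shared effect of period, but the standard error rises to 82 × √(2 × (1/10 + 1/20)) = 44.9 mg. The detectable difference is then 2.802 × 44.9 ≈ 126 mg (normal approximation), or 46% of 274 mg.

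**The case against.** The strongest reply is that finding a dose is not an aim. The Objective is a randomised efficacy comparison. Specific Aims 1.1 to 1.4 cover effect, pharmacokinetics, genotype and caregiver factors. The sample size serves pooled methadone against control. No stated primary analysis fails because of the label. This stands, and it limits the point to the label and to what may be concluded about dose.

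A second reply is that the word 'modified' permits departures from the classical subject-by-subject method. It does, but the modification is never described. Amendment 3 shows that the dose range was reconsidered on observations during the trial; it gives reasons but no criterion.

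Three stronger readings are tempting, and the documents do not support them.

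- *That only methadone-versus-control contrasts are possible.* Section 2 proposes to compare two doses and study a dose effect, and 9.3.2 provides for comparison across two or three groups. The between-dose contrast is weak and tied to calendar period, but it is planned and can be done.
- *That the trial must end after one step with no reversal.* Section 6.1 allows further cohorts. Even so, without a response or a rule, more cohorts would not make it an up-and-down design.
- *That the dose step has a calculable error rate.* One could treat a significant cohort result as the step signal and turn the 70% power into an error rate. The plan contains no such rule and gives no cohort size, so that figure would describe a procedure nobody has specified.

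**Conclusion.** The label is unsupported. The trial described is a randomised comparison in sequential dose cohorts, and under this plan no ED50, effective dose or optimal dose can be estimated. That conclusion rests on reading the design, outcome and analysis sections, not on a calculation.

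The primary comparison of methadone with control stands. A reader might infer that the missing dose-finding machinery undermines it; the pooled power shows that it does not.

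The between-dose comparison can only be exploratory, for two reasons. First, the smallest difference it can detect with 80% power is about 74.5 mg, assuming 20 patients per dose and the pilot SD. Second, the doses come in successive periods, and Amendment 3 reports that postoperative pain management, including gabapentin and methocarbamol, has changed since the group's previous study. Amendment 3 does not date that change against the cohorts, so the confounding is a risk and its size is unknown.

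**What to change.** - **Synopsis and Section 6.1:** replace the Dixon dose-finding label with 'randomised controlled trial in sequential dose cohorts', and remove the citation attached to it.
- **Section 9.3.2, add:** 'For each methadone dose given, the difference from the concurrent controls of the same cohort will be reported with a 95% confidence interval. The comparison between doses is exploratory, because the doses are studied in successive periods and the sample size does not support it. A non-significant difference between doses will not be taken as equivalence. No effective or optimal dose will be claimed.'

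The cost is wording in three places. The dose-finding claim is given up; the planned between-dose comparison stays. Doses, allocation, sample size and patient care do not change. Relabelling does not supply the missing timing, content and criterion of the interim analysis, which remain for the sponsor to document.
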